3.2 Study duration and duration of subject participation

Six months are expected to be needed to obtain all ethical and official clearances. With 3 active sites, recruitment period shall last 12 months, with possible extension up to 18 months depending on recruitment capacity. The follow-up period will be 12 months. In addition,

patients will be further assessed for their clinical and parasitological outcome at 24 months follow-up visit.

Therefore, the overall study duration is expected to be 36-42 months from first patient in (FPI) to last patient out (LPO). Taking into account the analysis and reporting period, the study shall last 42-48 months.

3.3 Rationale of study design

Combination treatment is well accepted in the treatment of VL, paromomycin (PM) combined with miltefosine in Asia; or SSG combined with PM for example in East Africa and may offer shorter duration of treatment thus preventing prolonged hospitalization. Another possible advantage is prevention of development of resistance and reduced cost. These principles also apply to PKDL, where the need for an ambulatory treatment with a highly safe, efficacious and user-friendly regimen is even more pressing as patients are not ill, except for the rash.

This study aims primarily to improve current treatment options. In addition, this will be the first study ever in PKDL in which outcome will be described in clinical, parasitological and immunological terms in relation to pharmacokinetics thus providing the rationale and focus for subsequent studies.

The present protocol will have estimation of pharmacokinetics levels and drug levels in skin after administration of treatment. Pharmacodynamic parameters of repeated qPCR measurements in blood and in tissue at baseline, EOT, and at the 3, 12 months follow-up visits, and skin qPCR at 24 month follow up visit will be assessed to allow for a simultaneous population PK-PD analysis to investigate in detail the drug exposure-treatment response relationship.

4 Selection of Subjects

A total of 126 patients will be included in this study. Patients will be recruited at following sites: Surya Kanta Kala Azar Research Centre (SKKRC), Mymensingh in Bangladesh; and two sites in India at KAMRC Muzzafarpur and RMRI, Patna. Sites will be notified when the maximum number of patients to be recruited is reached in the study.

The average number of PKDL patients treated at each site are as follows: KMRC-4-5 patients/month, RMRI-10-15 patients/month and Mymensingh-4-5 patients/month.

Considering a potential of 20 PKDL confirmed cases per month and a conservative estimation of 50% of these cases meeting inclusion and exclusion criteria for the study, there will be 10 patients enrolled/month and recruitment will be completed in 10-12 months. As mentioned above, this is based on historical data, and recruitment may take longer, up to 18 months.

The following eligibility criteria were designed to select subjects for whom the protocol treatment is considered appropriate. All relevant medical and non-medical conditions should be taken into consideration when deciding whether this protocol is suitable for a particular subject. Eligibility criteria may not be waived by the investigator. Any questions regarding a subject's eligibility should be discussed with the DNDi Clinical Manager prior to subject's enrolment.

4.1 Inclusion criteria

Subjects must meet all of the following inclusion criteria to be eligible for enrolment into the study:

- Confirmed PKDL case by clinical presentation and demonstration of parasites by microscopy in a skin smear or biopsy or by PCR, with stable or progressive disease for at least 4 months
- Male or Female patients aged 6 to 60 years
- Written voluntarily informed consent from adult patient and from parent / guardian in case of children <18 years old. In the case of minors, assent from the children will also be obtained according to country regulations.

4.2 Exclusion criteria

The presence of any of the following will exclude a subject from study enrolment:

- Patients who had prior treatment of PKDL within last 2 years.
- Pregnant and lactating women and women of childbearing age (12 to 55 years) who, before randomization, cannot be assured contraceptive cover during treatment and 5 months thereafter
- Patients with sign and symptoms of severe diseases: defined as suffering from a concomitant severe infection such as TB or any other serious known underlying disease (cardiac, renal, hepatic)
- Severe malnutrition defined by BMI for age WHO reference curves for gender, Z score
 -3 for subjects 6 19 years; BMI < 16 for subjects > 19-years old
- Patients with haemoglobin < 5g/dL
- Patients with abnormal liver function (ALT and AST) tests of more than three times the normal range.
- Patients with total bilirubin levels >1.5 times the upper normal range
- Patients with serum creatinine above the upper normal range
- Patients with serum potassium < 3.5 mmol/L
- Patients with a positive HIV test as applicable
- Patients / guardian not willing to participate
- Patients with history of allergy or hypersensitivity to the relevant study drug
- Patients on immunomodulators

Women who are sexually active and not using an assured method of contraception i.e. either IUCD or medroxyprogesterone acetate (Depo-Provera) but who wish to participate in the trial must sign an additional consent form and agree to receive a long-acting assured form of contraception medroxyprogesterone acetate (Depo-Provera). One injection (which is effective for 3 months) will be administered at baseline, and a 2nd injection will be administered at 3 months visit. This is needed to ensure adequate coverage taking into account the long half-life of approximately 7 days of Miltefosine. Oral contraceptives are not considered adequate

in this context because of the high prevalence of vomiting and diarrhea associated with miltefosine treatment.

Note: Patients not suitable for inclusion in the trial but with confirmed PKDL cases will be treated at the trial sites following National Program treatment policy for PKDL cases.

5 Schedule of events

Protocol activities	Screening	Screening Tre			iod	EOT		Follow-up period			
	D-28 to D0	D1	D8	1 day) D15	D22ª	D30 (+/- 3 days)	3M (+/- 7 days)	6M (+/- 7 days)	12M (+/-14 days)	24M ^f / EOS (-1month/+3 months)	
Consent form	х									х	
Inclusion and Exclusion criteria	х										
Vital signs and physical exam	х	х	х	Х	х	х	х	х	x	x	
Demographic data and Medical history	х										
Pregnancy test	х										
HIV test	x										
rK 39 test	х										
CBC, ALT / AST, Creatinine, Potassium, bilirubin	x		х	Х	х	x	Xp	x ^b	x ^b		
Skin snip for microscopy and qPCR	x					x	х		X	x	
Blood PD (qPCR)	х					х	х		х		
Tape disc skin sample for qPCR	х					х	х		Х		
Skin biopsy for PK				xc	Xa						
Plasma sample for Miltefosine PK ^a			х	Х	х	х	х				
Plasma sample for Ampho B		х		Х	х	x					
Blood sample for immunological parameters	х			Х		х	х		х		
PKDL evolution assessment, including photographs	х					х	х	х	х	x	
Ambisome monotherapy treatment			Amb injections: D1, D4, D8, D11, D15							1	
Ambisome + miltefosine treatment		Amb injections: D1, D4, D8, D11, D15 + Milt allometric D1-D21									
Safety assessment	SAEs and study related AEs		SAEs and AEs monito							nd AEs related to r procedures	

Protocol Version/Date: V3.0, 25 Feb 2020

a) Assessments to be performed only for the Ambisome® + Miltefosine arm

b) Only if abnormal at the previous assessment in a scheduled or unscheduled visit

c) Day 15 skin biopsy sample only for the Ambisome® monotherapy arm

d) A total of 30 subjects per arm will be included in the Ampho B PK assessment. Day 1 sampling to be performed at the end of infusion and at 2, 4, 8 and 22 hrs after the end of infusion. Day 15 sampling to be performed prior to infusion, at the end of infusion and at 2, 6 and 22 hrs after the end of infusion. One single sample to be collected at D22 for the Ambisome+miltefosine combination arm. One single sample to be collected at D30 for the Ambisome monotherapy arm. f. If the patient has completed 24 months /EOS before the approval of Protocol Amendment V3.0, 25 Feb 2020, the patient can be called as soon as possible for the final visit, this won't be considered a protocol deviation.

6 Enrolment procedures

A computer generated, randomization code will be used for patient treatment allocation to one of the two treatment arms. One set of individuals, opaque, sealed and sequentially numbered envelopes will be provided to the treatment sites, one envelope per patient. Eligible patients who fulfil all the inclusion criteria and have none of the exclusion criteria, and from whom informed consent has been obtained, will be randomized to one of the treatment regimens using the sealed envelopes.

The patient receives the treatment written on the card inside. The card must then be placed back in the envelope and retained for drug accountability and monitoring purposes. This method of treatment concealment will minimise selection bias as the investigator will not know the allocation of treatment for a specific patient until the envelope is opened.

7 Study treatments

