In the Miltefosine regimen, treatment may be temporarily interrupted (due to AEs or at the discretion of the investigator) and resumed if this interval is no longer than 72 hours. Once resumed, the subject will complete the 21 days of treatment by prolonging the treatment up to Day 24 (missing doses will be compensated). In this case, the total administered dose will still be within the 90% range of full compliance, therefore it will not be considered a compliance deviation.

If treatment needs to be interrupted for > 72 hours due to an AE, rescue treatment will be considered, at the discretion of the investigator.

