7.8 Rescue and Escape treatments

At any time-point during the study, if the patient does not respond to treatment, or lesions are worsening, or if after the healing period, the lesions reappear/reactivate, rescue treatment can be initiated at the discretion of the study investigator. A subject who receive rescue treatment at any time during the trial will be considered a treatment failure and will be withdrawn from the study. Rescue treatment will be provided to the patient as per standard recommendations by National Program with Miltefosine monotherapy for 12 weeks.

Patients will be given rescue treatment if:

- Progression of the disease is documented at any point in time during the study treatment or FU, and rescue treatment is indicated by the investigator
- They fail to tolerate trial medication or if occurrence of adverse event(s) during receipt of test drug dose (refer to the Ambisome[®] pack insert for withdrawing the patients) requires permanent interruption of treatment, and rescue treatment is indicated by the investigator
- If after healing period lesions reappear/reactivate

8 Study Assessments

8.1 Timing of Assessments:

Study assessments will be performed at baseline, D1, D8, D15, D22 (only for subjects allocated to combination arm), and D30 (EOT, +/- 3 days) during treatment phase.

All subjects will have follow-up visits at 3 months (+/- 7 days), 6 months (+/- 7 days) and 12 months (+/- 14 days) after the onset of treatment to assess efficacy and safety. A strategy will be put in place according to the context of each trial site to assure patients comply with the schedule of scheduled study visits. This will include active tracking of the patients through telephone contact or domiciliary visits.

In addition, a follow-up visit will be performed at 24 months (-1 month/+3 months) to assess the long-term response to treatment and safety. All patients will be invited to present to the 24 months follow-up visit, except those who have been withdrawn from the trial [e.g. for safety reasons (AE leading to treatment discontinuation and rescue treatment received), patients who withdrew consent, and cases of death, or patients who were treatment failure (received rescue treatment at any time during the 12 months follow-up period, including at 12 months visit).

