8.2 Baseline Assessments

The following baseline assessments will be done during screening (-28 days to day 0) and after having obtained Informed Consent in order to confirm PKDL diagnosis and verify inclusion and exclusion criteria.

- Demographic data including age and gender
- Medical history including relevant past history, previous VL episode, previous history of PKDL, concomitant medications
- Clinical examination: Physical examination including clinical signs, skin lesions, PKDL assessment, body weight, height, vital signs (Temperature, Heart rate and Blood pressure), spleen and liver size
- Clinical safety laboratory evaluations:
 - Haematology: CBC, including total WBC with differential, platelets
 - Biochemistry: Alanine aminotransferase (ALT), Aspartate aminotransferase (AST), total bilirubin (TBIL), Creatinine (CRE), Potassium
 - Pregnancy test

- HIV test routine counselling for HIV test will be given for patients or patients' parents in case of minors, as part of the study informed consent procedure interview or a separate consent will be requested, according to the local requirements. Testing will be done according to national guidelines and undergo a single rapid diagnostic test for the purposes of the clinical trial. If the RDT for HIV is positive, the patient must be excluded from participating in the clinical trial and receive current standard treatment for PKDL and further assessment and treatment for HIV according to the national HIV treatment Guidelines.
- o rK 39 test
- Skin snip sample for parasitological examination by microscopy and pharmacodynamics assessment (qPCR)
- Blood sample for pharmacodynamics assessment (qPCR)
- $\circ~$ Blood sample for immunological parameters assessment (cytokines IL-2, IFNY, TNFa, IL-10, and Granzyme B)
- Photograph of the patient as per SOP (front and back side with lesions)

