8.6.10 Exposure in utero

All pregnant women are excluded from the trial. This is specifically due to the teratogenic potential of miltefosine (demonstrated in rats). The manufacturer and Sponsor recommend that effective contraception should be used during and up to 5 months after treatment of miltefosine.

If any trial subject becomes or is found to be pregnant within the initial 6 months of her participation in this trial the investigator must submit the event on the Pregnancy Report form. This must be done irrespective of whether an adverse event has occurred. The information submitted should include the anticipated date of delivery.

The investigator will follow the subject until completion of the pregnancy or until pregnancy termination (i.e., induced / spontaneous abortion). The investigator will provide pregnancy outcome information in the Pregnancy Outcome report form.

A pregnancy is not an SAE.

In the case of a live birth, a pediatrician should assess the infant at the time of birth and submit a Child report. An SAE should be declared in the case of unfavourable pregnancy outcome (abortion, still birth) or congenital abnormality. In case of *in utero* exposure, the parents will be proposed a follow-up of the new-born up to the age of 2 years old.

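### Section 4.2 ties the second contraceptive injection to the 3-month visit and not to the first injection, so a late in-window visit can fall up to about 7-8 days after the first injection's stated cover ends

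*Protocol*

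**What the plan says.** Protocol section 4.2 excludes women of childbearing age "who, before randomization, cannot be assured contraceptive cover during treatment and 5 months thereafter". Section 8.6.10 repeats the period as the recommendation of the manufacturer and the sponsor: "effective contraception should be used during and up to 5 months after treatment of miltefosine".

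Women who are sexually active and use neither an IUCD nor the injectable may join if they sign an additional consent form and accept the injectable. For them section 4.2 states: "One injection (which is effective for 3 months) will be administered at baseline, and a 2nd injection will be administered at 3 months visit". It then gives the purpose: "This is needed to ensure adequate coverage taking into account the long half-life of approximately 7 days of Miltefosine".

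Section 8.1 places the follow-up visits "at 3 months (+/- 7 days), 6 months (+/- 7 days) and 12 months (+/- 14 days) after the onset of treatment". The schedule of events (section 5) shows the miltefosine course as "Milt allometric D1-D21". Section 7.2 allows for an interruption of up to 72 hours, after which "the subject will complete the 21 days of treatment by prolonging the treatment up to Day 24".

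**The concern.** The two injections are timed on different clocks. The first injection's 3 months run from the day it is given. The second is due at a visit that is counted from treatment onset and has its own window. As far as the visible text goes, no rule says that the second must be given before the first runs out, and the schedule of events as read has no row for either injection.

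A site can therefore give both injections when section 4.2 says, at visits inside their windows, and still pass the end of the first injection's stated effect before giving the second. Those days lie inside the period that the protocol itself sets for a drug it describes as teratogenic. The sentence that is meant to secure the cover does not quite secure it.

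**Working it through.** **Inputs**
- Effect of one injection: 3 months (section 4.2).
- Cover required: treatment plus 5 months (sections 4.2 and 8.6.10).
- 3-month visit: from treatment onset, D1, with a window of 7 days either side (section 8.1).
- Last miltefosine dose: D21 as scheduled (section 5), D24 at the latest after an interruption (section 7.2).
- Miltefosine half-life: about 7 days (section 4.2).
- Assumed: 3 months = 91 days and 5 months = 152 days, unless calendar months are named. D0 is the day before D1.

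**Step 1: the plan as intended.** First injection on D1, visit on time.
- Second injection: 1 + 91 = D92, the day the first injection's cover ends, so the gap is 0.
- Cover from the second ends: 92 + 91 = D183.
- Cover required to: 21 + 152 = D173, or 24 + 152 = D176 after an extension.
- Margin: 10 days, or 7 days after an extension (8-11 and 5-8 days by calendar months).

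Two injections are therefore enough in total, and the plan works when the visit is on time.

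**Step 2: the gap at the second injection.** Let b be the day of the first injection and L the days by which the visit is late.
- Visit day = 1 + 91 + L, so the window runs from D85 to D99.
- First cover ends on day b + 91.
- Gap = max(0, (92 + L) - (b + 91)) = max(0, 1 - b + L).

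| Visit | First injection D1 | First injection D0 |
|---|---|---|
| 7 days early (D85) | 0 | 0 |
| On time (D92) | 0 | 1 |
| 3 days late (D95) | 3 | 4 |
| 7 days late (D99) | 7 | 8 |

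The single day in the on-time D0 cell is a matter of how days are counted.

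**Step 3: does the result depend on the length of a month?**
- Calendar months, visit 7 days late: 7 days (D1), 7-11 days (D0). On-time visit: 0 (D1), 0-4 (D0). Early visit: 0.
- Drug effect and visit interval each taken as 90, 91, 92 days or calendar months, visit 7 days late: 4-10 days (D1), 5-11 days (D0).

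A gap on the last permitted day exists under every convention tried. For visits only a few days late it does not: since a D1 injection can give as little as 4 days at 7 days late, a visit 3 days late can leave none.

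**Step 4: where the gap lies.** With a first injection on D0 it starts on D91. That is before the required end at D173. It is also (91 - 21)/7 = 10 half-lives after the last scheduled dose; 2 to the power -10 is about 0.1%.

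**Step 5: bounds for a second injection that closes the gap.**
- Latest: 3 months after the first, D91 (from D0) or D92 (from D1).
- Earliest, so that cover reaches D176: 176 - 91 = D85 (D82-D86 by calendar months).

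The lower bound matters. By calendar months, a visit 7 days early after a D24 finish leaves between 3 days too few and 1 day to spare at the end.

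**The case against.** Several points on the other side are fair.

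- **The gap is a maximum.** A reader might infer that any late visit leaves a week uncovered. It does not: 7-8 days is the figure for the last permitted day, and a smaller delay leaves a correspondingly smaller gap. This stands.
- **Three months is a rounded duration.** Section 4.2 does not say that protection stops on day 91. What is shown is that the second injection can fall after the stated effect has ended; that a woman is then unprotected is inferred. This stands too. But the protocol states no grace period, and its rule has to be judged on the duration it gives.
- **The eligibility criterion governs.** Section 4.2 requires assured cover, section 4 says criteria may not be waived, and section 8.1 calls for active tracking to keep visits on schedule. A careful site would not let cover lapse. This makes a gap less likely, but the injection sentence is the operating instruction and its timing does not enforce the requirement.
- **The consent form.** The additional form for these women is not visible and may fix the dates. That is a real limit on confidence.
- **Little drug remains.** At about ten half-lives the residue is very small. A reader might infer a material foetal risk from the gap; the protocol's own half-life does not support that. The shortfall is against the 5 months that the protocol chose.

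A reader might also infer a gap of several weeks, because section 8.2 opens: "The following baseline assessments will be done during screening (-28 days to day 0". That section lists assessments, and the injection is not among them. Reading it as permission to inject at the start of screening is strained, and the point does not rest on it.

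**Conclusion.** The point holds in a limited form. The two-injection plan supplies enough cover in total but does not guarantee that it is continuous. With a first injection on D0 or D1, an in-window late visit can fall up to about 7-8 days after the stated 3-month effect has ended (4-11 days on the last permitted day across the month conventions tried). There is no gap at an early visit and essentially none at the nominal one.

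This rests on taking the stated 3 months as the end of cover, and on there being no other timing rule in the consent form. It concerns combination-arm women who are not already using an IUCD or the injectable and whose 3-month visit is late. No endpoint, estimate or analysis changes. Severity is minor and confidence medium.

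**What to change.** In section 4.2, and as a row or footnote in the schedule of events, state that:

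- the first injection is given on D0 or D1, before the first miltefosine dose;
- the second is given no later than 3 months after the date of the first, and no earlier than about D85, so that cover runs without a break to 5 months after the last miltefosine dose, including a course extended to D24.

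This costs one sentence and one schedule entry. The second injection then falls between about D85 and D91 or D92, so some women will need it in the early half of the 3-month window or at a separate contact. If the additional consent form already fixes these dates, it is enough to bring section 4.2 into line with it.

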7.1 DNDi study treatment: Investigational Products

All investigational products will be supplied by the DNDi from commercially available stocks.

7.1.1 Name: Liposomal Amphotericin B (Ambisome®)

Class: a macrocyclic, polyene antifungal antibiotic produced by Streptomyces nodosus.

Mechanism of action: affects sterol biosynthesis, disrupting the parasite membrane.

Commercial source: Gilead.

Product appearance: Ambisome[®] comes as a sterile lyophilised powder in a 15ml sterile Type 1 clear glass vial containing a yellow powder with the active ingredient amphotericin B 50mg encapsulated in liposomes. The closure consists of a butyl rubber stopper and aluminium ring seal with a removable plastic cap. Vials are packed in cartons of 10, with 10 filters provided.

The total dose of Ambisome[®] treatment will be 20mg/Kg, given as 4mg/Kg/day over 5 administrations at D1, D4, D8, D11 and D15.

Administration:

• Add 12mL of water for injection to each Ambisome[®] vial, to yield a preparation containing 4mg/mL (do not use saline or any bacteriostatic agents).

Ambisome[®] is incompatible with saline and should not be mixed with other drug or electrolyte solutions during administration.

• Immediately after the addition of water, shake the vials vigorously for 30 seconds to completely disperse the Ambisome[®]. Visually inspect the vials for particulate matter and continue shaking until complete dispersion is obtained.

• The infusion providing from 2.00 to 0.20mg of amphotericin per mL is obtained by dilution with 1 to 19 parts respectively by volume of 5% dextrose injection.

• Calculate the volume needed based on the dose of 4mg/Kg, according to patient's weight. Withdraw the calculated volume of reconstituted Ambisome[®] into a sterile syringe.

• Using the 5 micron filter provided, instil the Ambisome[®] preparation into a sterile container with the correct volume of dextrose injection.

